5.4.2.4 Progression-free Survival on Next Line of Therapy

PFS2 is defined as the time from randomization to the date of disease progression on next line of therapy or death, whichever comes first.

Subjects who started the next line of therapy and have not yet progressed on the next line of therapy and are still alive will be censored on the last date they are known to be alive. Subjects who did not have any new anticancer therapies and had no death documented before the data cutoff date will be censored at the last date they are known to be alive.

Determination of date of PFS2 event or censoring is summarized in Table 7 below.

Table 7 PFS2 Event and Censoring Method

Situation	Date of Event or Censoring	Outcome
Subjects who started the next line of therapy and have not yet progressed on the next line of therapy and are still alive	Date of last known to be alive	Censored
Subjects who did not have any new anticancer therapies and had no death documented before the data cutoff date	Date of last known to be alive	Censored
Disease progression on the next line of therapy or any death	Minimum of earliest date that indicates progression on the next line of therapy and date of death	PFS2 event
Other, such as: 
 ○ Lost to follow-up ○ Withdrawal of consent 	Date of last known to be alive	Censored

The analysis of PFS2 based on investigator assessment will be performed on Per-Protocol Analysis Set 1. The median PFS2 will be estimated using the Kaplan–Meier method and presented with 2-sided 95% CIs. The hazard ratio of lenvatinib 14 mg over lenvatinib 18 mg and the corresponding 90% CIs will be estimated using the Cox regression model with Efron's method for ties, stratified by MSKCC prognostic group and prior PD-1/PD-L1 treatment. The Kaplan-Meier curve of PFS2 will also be plotted for each treatment arm.

Sensitivity analyses of PFS2 based on the Per-Protocol Analysis Set 2 and Full Analysis Set will also be performed in a similar manner.

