9.1.2.1 Treatment Period

The Treatment Period will begin with the first dose of study drug administration in Cycle 1 and continue in 28-day cycles until completion of the Off-Treatment Assessments (within 28 days after the last study drug administration). Subjects will undergo safety and efficacy assessments as defined in the Schedule of Procedures/Assessments (Table 6). Subjects will continue to receive study drug until confirmed disease progression, lost to follow-up, development of unacceptable toxicity, subject request, withdrawal of consent, or study termination by the sponsor. Subjects who discontinue treatment before the data cutoff for the primary analysis will enter the Follow-up Period and will be followed every 12 weeks (± 1 week) after the Off-Treatment Visit. If a clinic visit is not feasible, follow-up information may be obtained via telephone or email.

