9.1.2.2 Follow-Up Period

The Follow-Up Period will begin immediately after the off-treatment assessments have been completed and will continue as long as the study subject is alive, until the study subject withdraws consent, or until the data cutoff for the primary analysis. Subjects who discontinue study treatment before disease progression will continue to undergo tumor assessments every 8 weeks and as of Amendment 06, send these to the imaging core laboratory (ICL) until documentation of disease progression or start of another anticancer therapy. Following the Off-Treatment Visit, subjects will continue to be followed every 12 weeks (± 1 week) for survival and PFS2, and all anticancer treatments received will be recorded until the data cutoff for the primary analysis. This information will be recorded unless the information is not allowed to be provided due to confidentiality.

If a subject discontinues study treatment and does not consent to continued follow-up, the investigator must not access confidential records that require the subject's consent. However, an investigator may consult public records to establish survival status. Copies of tumor assessment scans will no longer be sent to the ICL and independent review will not be carried out during the Follow-Up Period.

All subjects who are still on study treatment following the data cutoff for the primary analysis (ie, at the end of the Randomization Phase) will continue to receive the same study treatment. Tumor assessments will be performed according to the local standard of care, but not less frequently than every 12 weeks or earlier if clinically indicated, and scans will no longer be required to be sent to the ICL. Subjects will continue to receive study treatment until confirmed disease progression, development of unacceptable toxicity, subject request, withdrawal of consent, lost to follow up or study termination by the sponsor. If the study is terminated by the sponsor, study drug (s) will be provided to subjects where commercial access is not available.

The Off-Treatment Visit will occur within 28 days after the final dose of study treatment. All AEs and SAEs will be captured up to 28 days after last dose of study drug (Table 7).

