- The Follow-up Period will begin immediately after the off-treatment assessments have been completed and will continue as long as the study subject is alive, until the study subject withdraws consent, or until the data cutoff for the primary analysis. Subjects who discontinue study treatment before disease progression will continue to undergo tumor assessments every 8 weeks and as of Amendment 06, send these to the imaging core laboratory (ICL) until documentation of disease progression or start of another anticancer therapy. Following the off-treatment visit, subjects will continue to be followed every 12 weeks (± 1 week) for survival and PFS2, and all anticancer treatments received will be recorded until the data cutoff for the primary analysis. This information will be recorded unless the information is not allowed to be provided due to confidentiality.

The data cutoff for the primary analysis will occur at the end of the Randomization Phase, which is defined as the time when all randomized subjects have completed Week 24 assessments or have discontinued study treatment prior to Week 24.

Subjects will continue to receive investigational product until they complete the off-treatment visit prior to their transition to commercial lenvatinib and everolimus or an access program. The last subject last visit for the End of Study will be the date of the off-treatment visit for the last subject.

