5.4.2.1 Progression-free Survival

DEFINITION

PFS is defined as the time from the date of randomization to the date of first documentation of disease progression based on investigator assessments or date of death, whichever occurs first.

Determination of the date of PFS event or censoring is summarized in Table 5 below.

Table 5 PFS Event and Censoring Rules

No.	Situation	Date of Progression or Censoring	Outcome
1	No baseline or postbaseline adequate tumor assessments	Date of randomization	Censored
2	Progression documented between scheduled visits, on or prior to new anticancer therapy [#] and within 28 days after the last dose of study treatment	Date of first radiologic PD assessment	PFS Event
3	No progression at the time of data cutoff	Date of last adequate radiologic assessment on or prior to data cutoff	Censored
4	New anticancer therapy started	Date of last adequate radiologic assessment on or prior to the start of new anticancer therapy	Censored
5	Death before first PD assessment, on or prior to start of new anticancer therapy [#] and within 28 days after the last dose of study treatment	Date of death	PFS Event
6	Death between adequate assessment ^{#,*}	Date of death	PFS Event
7	Death or progression after more than one missed visit/tumor assessment ^{**}	Date of last adequate radiologic assessment before missed tumor assessments	Censored
8	Death or progression after 28 days from the last dose of study treatment	Date of last adequate radiologic assessment before the date of last dose of study treatment + 28 days	Censored
9	No progression and treatment discontinuation for reasons other than PD	Date of last adequate radiologic assessment before treatment discontinuation (ie, within last dose date + 28 days)	Censored

Note:

If documented PD and/or death occurs after the last dose, it is counted as a PFS event as long as the PD and/or the death occurs within 28 days since the date of the last dose of study treatment and provided that it does not violate other censoring rules (eg, start of new anticancer therapy before the PD or death). Otherwise the subject will be censored on the date of the last tumor assessment before the date of last dose of the study treatment.

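### PFS2 is censored at the date last known alive even where only survival was known, so for those subjects time with unknown progression status counts as progression-free

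*SAP*

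**What the plan says.** The endpoint is defined in SAP 5.4.2.4: "PFS2 is defined as the time from randomization to the date of disease progression on next line of therapy or death, whichever comes first". Protocol 9.7.1.1.2 leaves the PFS2 censoring rules to the SAP.

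SAP 5.4.2.4 and Table 7 then use one censoring date throughout:

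- Subjects on a next line who have not progressed on it and "are still alive will be censored on the last date they are known to be alive".
- Subjects with no new anticancer therapy who "had no death documented before the data cutoff date will be censored at the last date they are known to be alive".
- The row headed Other, which covers loss to follow-up and withdrawal of consent, also takes the date last known alive.

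Follow-up after treatment is described in protocol 9.1.2.2. Subjects are contacted every 12 weeks (±1 week) "for survival and PFS2, and all anticancer treatments received will be recorded until the data cutoff for the primary analysis". Contact can be remote (9.1.2.1): "If a clinic visit is not feasible, follow-up information may be obtained via telephone or email". If a subject stops treatment and refuses continued follow-up, records that need consent are closed to the investigator. The section then adds: "However, an investigator may consult public records to establish survival status". The protocol synopsis says the same.

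**The concern.** A PFS2 event can be either progression on next-line therapy or death. A censoring date for such an endpoint should be one up to which both were observable. The date last known alive meets that standard for death only. If it comes from a survival lookup after disease follow-up has stopped, the subject stays in the risk set over a period in which progression could not have been recorded and only death could count.

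The SAP applies a different standard to its other progression endpoints. For a PFS subject without progression at cutoff, Table 5 reads "Date of last adequate radiologic assessment on or prior to data cutoff". Duration of response (5.4.3.1) is censored at the last tumor assessment. The date last known alive also appears in the OS rules (5.4.2.3) for lost or withdrawn subjects, where it is right because death is the only event.

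At stake are the Kaplan-Meier median for PFS2 and the stratified Cox hazard ratio that SAP version 2.0 added.

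**Working it through.** **No plan figure to reproduce.** The documents state no expected PFS2 median, event count or rate of survival-only follow-up. Every input below is assumed, and the share of affected subjects is varied.

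**Inputs.** Progression on next line and death are independent and exponential. Scenario A has medians of 16 and 25 months, scenario B 20 and 30 months. Follow-up to cutoff is uniform from 6 to 36 months. A fraction f loses disease-status follow-up at a uniformly distributed time, independent of outcome, while vital status stays known to cutoff. Each run has 200,000 subjects.

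**Closed-form check.** The median of the earlier of two independent exponential times is 1/(1/m1 + 1/m2).

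- A: 16 × 25/41 = 9.76 months (simulated 9.71).
- B: 20 × 30/50 = 12.0 months (simulated 11.94).

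**Why the bias is upward.** In the gap the SAP rule can register only deaths.

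- A: ln2/25 = 0.028 per month against a true PFS2 rate of ln2/9.76 = 0.071, or 39%.
- B: ln2/30 = 0.023 against ln2/12 = 0.058, or 40%.

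**Kaplan-Meier median in months under three rules:**

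| f | A: SAP rule | A: last PFS2 contact | A: last contact, all deaths kept | B: SAP rule | B: last PFS2 contact | B: last contact, all deaths kept |
|---|---|---|---|---|---|---|
| 0% | 9.71 | 9.71 | 9.71 | 11.94 | 11.94 | 11.94 |
| 5% | 9.80 | 9.70 | 9.69 | 12.07 | 11.94 | 11.89 |
| 10% | 9.90 | 9.70 | 9.66 | 12.22 | 11.93 | 11.84 |
| 20% | 10.11 | 9.70 | 9.62 | 12.49 | 11.93 | 11.75 |
| 30% | 10.33 | 9.71 | 9.58 | 12.81 | 11.93 | 11.66 |

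The SAP rule overstates the median by 0.19 months (A) and 0.28 months (B) at f = 10%, and by 0.40 and 0.55 months at 20%. Censoring at the last PFS2 contact, with later deaths not counted, recovers the true median. Moving only the censoring date back while still counting deaths found later biases the median slightly downward, so deaths and censoring must rest on the same information.

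**Other assumed inputs.** With true medians of 12 or 15 months and a median of 8 months from progression to death, the overstatement is 0.3 to 0.5 months at 10% and 0.7 to 1.0 at 20%. With true medians of about 18 to 20 months it is about 0.4 and 0.8 to 0.9. The range over all sets is about 0.2 to 0.5 months at 10% and 0.4 to 1.0 at 20%.

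**Treatment comparison.** In scenario A with no true difference, the ratio of event rates (14 mg over 18 mg) is 0.999 when f is 10% in both arms, 0.984 at 10% against 5%, and 0.955 at 20% against 5%.

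**The case against.** The strongest reply is that few subjects are affected. Routine contacts collect survival and PFS2 together, so for anyone still in follow-up the last-alive date is normally also the last PFS2 date. A lost or withdrawn subject with no later lookup has no gap either. Under the public-records route, a gap arises only if the subject refuses follow-up, the investigator uses an optional lookup, and the subject is found alive at a later date. This stands. It limits the size and places the problem mainly in the Other row. A reader might infer from the uniform date rule that every censored PFS2 subject is biased; the documents do not support that.

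The no-new-therapy row is also defensible where absence of therapy is confirmed, because only death can then be a PFS2 event. That stands too, although a public record cannot supply the confirmation.

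A reader might also take the confidentiality clause in SAP 3.2 as a second source of survival-only follow-up: "This information will be recorded unless the information is not allowed to be provided due to confidentiality". The text does not go that far. Footnote s to protocol Table 6 attaches the exception to anticancer therapy records, and withheld treatment details do not show that progression status was unknown at a contact.

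Finally, the shift is small against sampling error. With 153 per arm and an assumed true median of about 15.5 months, 95% of simulated Kaplan-Meier medians fell between 12.6 and 19.0 months. That is true, but it does not justify a systematic bias that is cheap to remove.

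**Conclusion.** The point holds in a limited form. Table 7 permits a PFS2 censoring date that carries no progression information, and for subjects with survival-only data this pushes PFS2 upward. On assumed inputs the median is overstated by roughly 0.2 to 0.5 months if 10% of subjects are affected and 0.4 to 1.0 months if 20% are, with little effect if few are. These figures assume survival is traced to cutoff for all affected subjects and that loss of disease follow-up is unrelated to outcome. If that loss depends on prognosis, neither rule is unbiased.

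It is tempting to conclude that the hazard ratio is biased because the less tolerable regimen will lose more subjects. The documents do not establish this. Protocol 9.3.3 separates stopping treatment from withdrawing consent and keeps subjects who only stop treatment in PFS2 and survival follow-up. The hazard ratio is distorted mainly if the survival-only share differs by arm, and no such difference is documented.

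PFS2 is secondary and descriptive, with no formal test (SAP 5.3.3). Neither the ORR at 24 weeks non-inferiority test nor the primary safety test is touched.

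**What to change.** In SAP 5.4.2.4 and Table 7:

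1. Censor at the last contact at which PFS2 status was known, meaning either progression status on next-line therapy or confirmation that no next-line therapy has started. Do not use a vital-status-only date.
2. Do not substitute the last tumor assessment for untreated subjects. Scheduled scans stop at progression, so valid follow-up would be discarded while comparable deaths still counted. Runs on assumed inputs with complete follow-up put the resulting fall in the median at about 0.6 to 1.6 months.
3. State that, in the main PFS2 analysis, deaths learned only from survival lookup after PFS2 follow-up has ended are not events. The event row, which now counts any death, needs matching wording.
4. Keep the current last-known-alive rule, with all deaths counted, as a sensitivity analysis.

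The cost is SAP wording and one derived date from the 12-weekly contacts already scheduled, provided the case report form records the date and PFS2 status of each contact (the form is not among the documents). The price is slightly shorter follow-up and a few fewer events.

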5.4.3 Other Efficacy Analyses

Other efficacy analyses may be performed descriptively on duration of response (DOR), disease control rate (DCR), and clinical benefit rate (CBR).

5.4.3.1 Duration of Response

Duration of response is calculated from the date of initial documentation of the best overall response of CR or PR to the date of first objectively documented progressive disease or death, whichever occurs first, for the subjects who had achieved a best overall response of CR or PR.

Subjects who start new anticancer therapies without PD will be censored at the date of the last available tumor assessment prior to the start of new anticancer therapies. Subjects who have not progressed and subjects who did not die will be censored at the last tumor assessment date.

Analysis of DOR will be performed on the subjects who achieved a best overall response of CR or PR. Median DOR with 2-sided 95% CI will be estimated using the Kaplan-Meier method.

5.4.3.2 Disease Control Rate

The DCR is the proportion of subjects who achieved a best overall response of CR, PR or SD (minimum duration of SD ≥ 7 weeks). The DCR with corresponding 2-sided 95% CI based on the asymptotic normal approximation will be provided.

5.4.3.3 Clinical Benefit Rate

The CBR is the proportion of subjects who achieved a best overall response of CR, PR or durable SD (duration of SD ≥ 23 weeks). The CBR with corresponding 2-sided 95% CI based on the asymptotic normal approximation will be provided.

5.4.4 Subgroup Analysis for Efficacy/Safety Endpoints

To assess the internal consistency and investigation of homogeneity of the treatment effect across subgroups, subgroup analyses for the efficacy endpoint of ORR based on the investigator assessment and primary safety endpoint of proportion of subjects with intolerable Grade 2 or any \geq Grade 3 TEAEs within 24 weeks after randomization based on predefined subgroups specified in [Section 5.3.4](#) will be conducted.

Forest plots of subgroup analyses will be generated.

Additional subgroup analyses may be performed for selected efficacy and/or safety endpoints.

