The FDA and Eisai both utilized these models to explore various exposure-response analyses for the time course of tumor burden (size) and dose-altering AEs to aid in the design of the current study.

The three cases modeled were: (Case 1) where lenvatinib starting doses less than 18 mg QD in combination with 5 mg QD everolimus were administered and doses were reduced as necessary to control AEs; (Case 2) where a lenvatinib drug holiday was incorporated into the dosage regimen; and (Case 3) Case 1 with the additional caveat that a subject's lenvatinib dose could be subsequently raised as long as the subject tolerated the current dose. Note that Study 205 followed Case 1.

[figure not shown]
The modeling results showed that in Case 1, lenvatinib daily doses less than 18 mg were less effective, ie, the simulated percent reduction in tumor size was less and occurred later than with the 18-mg dose (see Figure 3), and the predicted ORR_{24W} was lower.

* In combination with 5 mg QD everolimus.

Figure 3 Case 1 – Effect Of Starting Dose Levels Less Than 18 Mg Lenvatinib* With No Allowance For Lenvatinib Dose Escalation

[figure not shown]
In Case 2 (see Figure 4), the efficacy of regimens utilizing a lenvatinib drug holiday proved less effective than continuous dosing, and the predicted ORR_{24W} was lower.

* In combination with 5 mg QD everolimus.

Figure 4 Case 2 - Simulated Average Tumor Reductions With Starting Dose Of 18 Mg Lenvatinib* With And Without Drug Holiday (One Week Break In Lenvatinib Administration After Two-Week Continuous Lenvatinib Administration With Continuous Everolimus Administration)

In Case 3 (see [Figure 5](#)), the efficacy of regimens that utilize lower starting doses (ie, 12 mg or 14 mg) but allow up titration of doses showed equivalent or superior tumor reduction and comparable predicted ORR_{24W} to an 18-mg starting dose that only allowed dose reduction of lenvatinib.

* In combination with 5 mg QD everolimus.

Figure 5 Case 3 - Simulated Average Tumor Reductions With Lenvatinib* Dose Escalation

Simulations of the 2 dose regimens to be investigated in this study suggest that the 14-mg lenvatinib starting dose (while maintaining the 5-mg QD everolimus dose) can also result in fewer dose reductions (see Figure 6).

Starting Dose: 18 mg w/o dose escalation

Starting Dose: 14 mg w/ dose escalation

[figure not shown]

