5.3.4 Examination of Subgroups

In general, subgroup analyses on the prespecified subgroups in Table 4 will be performed for the efficacy endpoint ORR based on the investigator assessment and the primary safety endpoint of proportion of subjects with intolerable Grade 2 or any \geq Grade 3 TEAEs within 24 weeks after randomization.

Exploratory analysis on the subgroup of subjects previously treated with PD-1/PD-1 will be performed and is specified in the [Section 5.8.2](#).

Additional subgroup analyses may be performed as appropriate.

Table 4: Subgroup Analyses for Efficacy and Safety Endpoints

Subgroup	Definition
Sex	Male, Female
Age	<65, ≥ 65 years

Race	White, Non-White
Region	Eastern Europe, Western Europe, North America, Asia/Pacific
Baseline hypertension status	Yes, No
MSKCC risk group	Favorable, Intermediate, and Poor risk
Prior PD-1/PD-L1 treatment	Yes, No

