5.4.1 Primary Efficacy Analyses

The primary efficacy endpoint ORR_{24W} is defined as the proportion of subjects with BOR of CR or PR as of the Week 24 (after randomization) timepoint based on investigator assessments, during treatment or within 28 days after the last dose date but on or prior to the start of new anticancer therapy. Subjects with responses achieved after the start of new anticancer therapy or after 28 days from the last dose date will not be considered as responders.

The primary analysis of ORR_{24W} will be based on a non-inferiority test. The study hypothesis is that the ORR_{24W} for lenvatinib 14 mg QD in combination with everolimus 5 mg is non-inferior to the ORR_{24W} for lenvatinib 18 mg QD in combination with everolimus 5 mg in subjects with renal cell carcinoma following one prior VEGF-targeted treatment.

For this study, the non-inferiority of lenvatinib 14 mg QD in combination with everolimus 5 mg relative to lenvatinib 18 mg QD in combination with everolimus 5 mg is defined using 70% retention of the treatment effect of lenvatinib 18 mg QD in combination with everolimus vs. everolimus, which translated to the estimated odds ratio =0.76 for the non-inferiority margin following the approach of [Rothmann et al. \(2003\)](#).

The non-inferiority hypothesis for ORR_{24W} with the non-inferiority margin of odds ratio =0.76 for the final analysis can be stated as follows:

H_0 : Odds ratio of $ORR_{24W-14mg}$ vs $ORR_{24W-18mg} \leq 0.76$

H_a : Odds ratio of $ORR_{24W-14mg}$ vs $ORR_{24W-18mg} > 0.76$ (non-inferiority)

The primary analysis of ORR_{24W} will be performed on the Per-Protocol Analysis Set 1. The point estimate of ORR_{24W} with the corresponding 95% CI for each treatment arm will be summarized. The odds ratio of ORR_{24W} (lenvatinib 14 mg over lenvatinib 18 mg) along with the 90% CI will be calculated using the CMH method stratified by MSKCC prognostic group and prior PD-1/PD-L1 treatment. Non-inferiority in ORR_{24W} will be claimed if the O'Brien-Fleming efficacy boundary is crossed. If the 1-sided P value is ≤ 0.045 at the final analysis, non-inferiority in ORR_{24W} will be claimed (interim analysis is specified in [Section 6](#)). The boundary P value ≤ 0.045 for the final analysis is based on the plan that the two interim analyses will take place when the total number of 150 subjects and 200 subjects in the Per-Protocol Analysis Set 1 have completed 24 weeks of follow-up or discontinued early.

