5.4.2.2 Objective Response Rate

ORR is defined as the proportion of subjects achieving a best overall response of confirmed CR or PR during treatment or within 28 days after the last dose date but on or prior to the start of new anticancer therapy at the time of clinical data cutoff. Subjects with overall responses achieved after the start of new anticancer therapy or after 28 days from the last dose date will not be considered as responders. Subjects who do not have a tumor response assessment for any reason will be considered non-responders and will be included in the denominator when calculating the response rate.

The point estimate of ORR and corresponding 95% CI based on asymptotic normal approximation will be summarized for each treatment arm. Odds ratio with 90% CI will be estimated using the CMH method stratified by MSKCC prognostic group and prior PD-1/PD-L1 treatment. In addition, the treatment difference in ORR between lenvatinib 14 mg and lenvatinib 18 mg will also be estimated along with 90% CIs based on the asymptotic

normal approximation.

A sensitivity analysis of ORR based on the Per-Protocol Analysis Set 2 and Full Analysis Set will be performed in a similar manner as described above.

In addition, waterfall plot for the percentage changes from baseline to postbaseline nadir (ie, best percentage changes from baseline) in sum of diameters of the target lesions will be presented. The depth of response for $>0\%$, $\geq 30\%$, $\geq 50\%$ and $\geq 75\%$ maximum reduction in sum of diameters will be summarized.

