5.8.2 Exploratory Analysis for Subjects with Prior PD-1/PD-L1 Treatments

Exploratory analysis on efficacy endpoints of PFS and OS may be performed descriptively for the subjects who had prior PD-1/PD-L1 treatments.

The subgroup analyses on the efficacy endpoint ORR and primary safety endpoint for the subjects with prior PD-1/PD-L1 treatment are specified in [Section 5.4.4](#).

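### The efficacy subgroup analyses use the secondary endpoint ORR and not the primary endpoint ORR24W, so they show only indirectly whether the tested effect is consistent across subgroups

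*SAP*

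**What the plan says.** SAP 5.3.4 states that the Table 4 subgroups (sex, age, race, region, baseline hypertension, MSKCC risk group, prior PD-1/PD-L1 treatment) will be analysed "for the efficacy endpoint ORR based on the investigator assessment and the primary safety endpoint". SAP 5.4.4 repeats the choice, planning "subgroup analyses for the efficacy endpoint of ORR based on the investigator assessment", and gives its purpose: "To assess the internal consistency and investigation of homogeneity of the treatment effect across subgroups". SAP 5.8.2 points back to it: "The subgroup analyses on the efficacy endpoint ORR and primary safety endpoint for the subjects with prior PD-1/PD-L1 treatment".

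The SAP treats ORR and ORR24W as two separate endpoints:

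- **ORR24W** is the primary efficacy endpoint (SAP 5.1.1, 5.4.1): "BOR of CR or PR as of the Week 24 (after randomization) timepoint based on investigator assessments".
- **ORR** is a secondary endpoint (SAP 5.1.2, 5.4.2.2). It counts a best confirmed response on treatment or within 28 days of the last dose, "on or prior to the start of new anticancer therapy at the time of clinical data cutoff". No week is fixed.

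In both definitions a response counts only on treatment or within 28 days of the last dose, and not after new anticancer therapy has started. They differ in the Week-24 limit.

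**The concern.** The stated aim is to check that the treatment effect is homogeneous. The effect that the trial tests is the ORR24W odds ratio: SAP 5.4.1 applies the 0.76 margin to it, and SAP 4 bases the boundaries and the 306 subjects on it. On the safety side the subgroup analyses use the primary 24-week endpoint. On the efficacy side they do not, and no reason is given.

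The two endpoints can part company in one direction. A subject whose first response comes after Week 24 is a non-responder for ORR24W and a responder for ORR. With scans every 8 weeks (Protocol 9.5.1.2), a delay of one scan can move a response past Week 24. If such late responses were more frequent with the 14-mg start in some subgroup, a shortfall at Week 24 would look smaller on the ORR plot, or vanish. At stake is how the subgroup results are read when the sponsor and the DMC weigh the totality of the data. The non-inferiority decision itself is not at stake.

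**Working it through.** **1. The plan's own figures belong to ORR24W, and they reproduce.**

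- Margin (SAP 4): exp(0.3 × log 0.395) = 0.757, stated as 0.76.
- Effect assumed for power: log[(0.45/0.55)/(0.37/0.63)] − log 0.76 = 0.332 + 0.274 = 0.606.
- Standard error at 153 per arm: √[1/(153 × 0.37 × 0.63) + 1/(153 × 0.45 × 0.55)] = 0.233.
- Power without interim looks: Φ(0.606/0.233 − 1.645) ≈ 0.83.
- Power with looks at 75, 100 and 153 per arm and the stated efficacy and futility boundaries, by simulation: 0.801, against the stated 80%. One-sided alpha with futility ignored: 0.050.

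**2. No analysis of ORR24W across the Table 4 subgroups is committed to.** SAP 5.4.1 analyses ORR24W in other analysis sets, with CRF strata, in a logistic model adjusted for center/region, on data from before the July 2018 unblinding and, conditionally, without 14-mg subjects who should have been up-titrated but were not. The center/region model adjusts for region and states no interaction with treatment. SAP 5.3.4 and 5.4.4 allow further subgroup analyses but name no endpoint for them.

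**3. How far the two endpoints can differ.** The documents give no late-response rates, so these are assumed. Take ORR24W of 30% (14 mg) and 37% (18 mg):

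OR = (0.30/0.70)/(0.37/0.63) = 0.73.

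Now add responses first seen after Week 24, in percentage points of all subjects:

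| Late responses, 14 mg / 18 mg | ORR, 14 mg vs 18 mg | Difference (points) | Odds ratio |
|---|---|---|---|
| none | 30% vs 37% | −7 | 0.73 |
| +3 / +3 | 33% vs 40% | −7 | 0.74 |
| +5 / +3 | 35% vs 40% | −5 | 0.81 |
| +8 / +3 | 38% vs 40% | −2 | 0.92 |
| +10 / +3 | 40% vs 40% | 0 | 1.00 |

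Equal late response leaves the picture almost unchanged. Full masking here needs more than three times as many late responses in the 14-mg arm (10 versus 3 points).

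**4. Precision within a subgroup.** Assume 50 per arm and 37% in both arms:

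- SE of the log odds ratio = √[2/(50 × 0.37 × 0.63)] = 0.414.
- 90% CI = exp(±1.645 × 0.414) = about 0.51 to 1.98.

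Both 0.73 and 1.00 lie well inside that interval.

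**The case against.** Most of the case on the other side stands, and it limits what can be concluded. A reader might infer any of the following, and the documents do not support them:

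- **That the ORR plots say nothing about consistency.** ORR is bounded by last dose + 28 days, new therapy and cutoff, and a subject who responds by Week 24 is in essence always an ORR responder too. A Week-24 shortfall shows on ORR unless late responses offset it.
- **That unequal follow-up biases the comparison.** Cutoff comes when all randomized subjects have completed Week 24 or stopped earlier (SAP 3.2), so early enrollees have a longer window. Allocation is randomized 1:1, however, so follow-up is expected to balance between arms. It raises the level of ORR and does not by itself distort the odds ratio.
- **That the protocol predicts delayed response in the 14-mg arm.** Protocol 7.2 does say that "lenvatinib daily doses less than 18 mg were less effective, ie, the simulated percent reduction in tumor size was less and occurred later", but this is its Case 1, without escalation. The 14-mg arm follows Case 3, with up-titration, for which the same section predicts tumor reduction at least as good as with the 18-mg start and a comparable ORR24W. Subjects who are not escalated because of toxicity do stay below 18 mg, but 18-mg subjects with such toxicity are reduced below 18 mg as well (Protocol 9.4.2.1). Nothing in the documents points to late response in a particular subgroup.
- **That the overall judgment would rest on the wrong measure.** Non-inferiority is decided on ORR24W, the subgroup plots enter no decision rule, and timing also shows in the PFS curves (SAP 5.4.2.1).
- **That a subgroup odds ratio below 0.76 would mean failure in that subgroup.** The margin and the power belong to the overall test in 306 subjects.

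The permission for additional subgroup analyses does not close the gap. It is optional, and choosing ORR24W after seeing the data would be post hoc.

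**Conclusion.** The point holds as a misalignment of limited size. Three SAP sections name the secondary ORR for the efficacy subgroups, while the section's stated purpose, the paired safety analysis and the primary test all point to the 24-week endpoint. The planned plot gives indirect evidence on the tested effect, not direct evidence. In the assumed example a Week-24 odds ratio of 0.73 appears on ORR as anything from 0.74 to 1.00, depending on how unequal the late responses are. The upper end needs a strong imbalance that the documents do not establish. The late-response rates and the subgroup size of 50 per arm are assumptions. Primary test, error rate, margin and sample size are unaffected. This is a cheap improvement worth making, not a flaw in the trial's main conclusion.

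**What to change.** - In SAP 5.3.4 and 5.4.4, name investigator-assessed ORR24W in Per-Protocol Analysis Set 1 as the efficacy endpoint of the Table 4 subgroup analyses and forest plot, with the odds ratio and the difference, each with a CI.
- Keep ORR as a second panel, so that a gap between Week-24 and later response is visible.
- Update the cross-reference in SAP 5.8.2 for subjects with prior PD-1/PD-L1 treatment.
- State that the results are descriptive and are not subgroup non-inferiority tests, because the intervals will be wide.

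The cost is a short SAP revision and one additional run of a forest plot that is already planned. No new data, alpha or subjects are needed.
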